## 3. SPECIFIC AIMS

**Aim 1.** To test, in a 16-session (26-week) randomized controlled trial of 72 adults with obesity and high levels of WBI, the effects on weight bias internalization (WBI) of the BIAS program combined with behavioral weight loss (BWL), in comparison to BWL alone.

*H1a: Participants who receive BWL + BIAS program will show significantly greater reductions in WBI after 12 weekly sessions than participants who receive BWL alone.*

*H1b: Participants in the BWL + BIAS program will continue to show greater improvements in WBI at 26 weeks (following an additional 2 biweekly sessions and 2 monthly sessions), compared to participants in the BWL group.*

**Aim 2.** To explore the effects of BWL + BIAS program, compared to BWL alone, on depression, perceived stress, health-related quality of life, and weight-related self-efficacy.

*H2: Participants in the BWL + BIAS program will show greater improvements in depression, perceived stress, health-related quality of life, and weight self-efficacy than participants in the BWL group at 12 and 26 weeks.*

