### 5.2 Inclusion/Exclusion Criteria

#### Key Inclusion Criteria

Eligible participants will be men and women ages 18-65 years. Participants must have obesity (defined as a BMI  $\geq 30 \text{ kg/m}^2$ ); report a history of experiencing weight bias as assessed by self-report questionnaire and in-person interview; and have elevated levels of WBI as indicated by an average score of 4 (midpoint) or above on the Weight Bias Internalization Scale (WBIS) and by in-person interview. Participants must be seeking weight loss. If currently taking medications, dosages must be stable for at least 3 months. Participants will be eligible to participate if they exhibit mild to moderate severity of depression, anxiety, or binge eating disorder, as determined by the behavioral evaluation and the screening measures (Beck Depression Inventory-II and Questionnaire for Eating and Weight Patterns; see below for details). Elevated WBIS scores are often associated with these variables. Participants taking anti-depressant medication will be eligible if their dose has been stable for a minimum of 3 months.

Eligible female patients will be:

- non-pregnant, evidenced by a negative urine dipstick pregnancy test
- non-lactating
- surgically sterile or postmenopausal, or they will agree to continue to use a method of birth control during the study

Participants must:

- have a PCP who is responsible for providing routine care
- have reliable telephone service with which to participate in conference calls
- understand and be willing to comply with all study-related procedures and agree to participate in the study by giving written informed consent

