## 7. STATISTICAL ANALYSIS

### 7.1 Sample Size Calculation

A power analysis was conducted for the **primary outcome: reduction in Weight Bias Internalization Scale (WBIS) scores at week 12**. Estimated group means, attrition rate, intraclass correlation (ICC), and variances were derived from data from prior studies conducted at our Center. Specifically, we predict a 12-week reduction of 1.5 points on the WBIS in the BWL + BIAS group and 1 point in the BWL group, with expected standard deviations of 1. Based on these estimates, a baseline sample size of 72 participants (36 per group), assuming a 20% attrition rate, will give us 95% power to detect a between-treatment group difference at week 12 of 1 point to be significant at alpha = 0.05. The power analysis was conducted using G\*Power 2. All secondary outcomes will be considered exploratory and will provide valuable findings that will help to inform larger studies. This study has not been powered to detect differences in changes in other psychosocial and behavioral outcomes, weight loss, and cardiometabolic outcomes.

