### 7.2 Analysis Plan

Data quality and integrity will be checked by assessing the data for missing and out-of-range values with basic statistical procedures, including univariate statistics and visual graphical displays (e.g., scatter plots). We will investigate all questions of data quality and integrity prior to performing any statistical modeling. To test the adequacy of randomization, preliminary analyses will include a comparison of all participant demographic and baseline characteristics by randomized treatment groups (t-tests or Wilcoxon rank sum tests for continuous variables and Chi-Square test or Fisher's Exact test for categorical data). If imbalances are observed, the relevant variables will be included as covariates in the final analyses.

All data will be analyzed under the intention-to-treat principle. Analyses will be two-tailed with a significance level of 0.05, and will be conducted using SPSS version 24.0 or SAS version 9.4. Participants who were randomized but did not attend a group meeting will not be included in the analyses, as they will not have received a dose of treatment. We will include as baseline covariates any variables that differ significantly between the treatment groups at baseline and show significant relationships with the outcome. To assess changes in WBIS scores across the 26-week trial, a mixed effects model will be fit with Treatment Group (*BWL+BIAS, BWL*) as a between subjects factor and Time (*Weeks 12 and 26*) as a categorical within-subjects factor. We will use the group x time interactions with the time main effect to estimate and test treatment group differences at each time point. In fitting a mixed effects model with residual maximum likelihood (REML), a variance-covariance structure must be selected. The criteria for selecting the best form of the variance-covariance structure will be based on criteria such as the Akaike's Information Criterion (AIC). The results from the mixed model will be summarized by mean (SE) for each treatment group at each time point. Residual analyses will be conducted to check for outliers and

influential points and violations in the normality assumption. If violations are detected, variance-stabilizing transformations will be considered.

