The second aim of assessing changes in other psychosocial and behavioral outcomes, and the secondary aims of assessing changes in weight loss and cardiometabolic risk factors, will be analyzed using the same methods as described above. Changes in all outcomes will be summarized by mean (SE) for each treatment group at each time point.

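### Screening WBIS is not a standing covariate in the primary mixed model; always adjusting for it, and naming the response, would give a modest gain in precision at almost no cost

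*Combined protocol and SAP*

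**What the plan says.** Section 7.1 names the primary outcome as "reduction in Weight Bias Internalization Scale (WBIS) scores at week 12", and hypothesis H1a in section 3 says that the combined arm "will show significantly greater reductions in WBI after 12 weekly sessions" than the comparator. Section 7.2 introduces the primary model with "To assess changes in WBIS scores across the 26-week trial, a mixed effects model will be fit with Treatment Group". Its terms are group, time with levels week 12 and week 26, and their interaction. Screening is not a level of time, and screening WBIS is not listed as a covariate.

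Two sentences in section 7.2 govern covariates:

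- "If imbalances are observed, the relevant variables will be included as covariates in the final analyses". No threshold is given.
- "We will include as baseline covariates any variables that differ significantly between the treatment groups at baseline and show significant relationships with the outcome". This requires two significant tests.

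The dependent variable is not named. Section 7.2 ends with "Changes in all outcomes will be summarized by mean (SE) for each treatment group at each time point", which again points to change.

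The WBIS is an eligibility measure (section 5.2: "as indicated by an average score of 4 (midpoint) or above") and is collected at screening (section 6.6), so a baseline value exists for everyone randomized.

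**The concern.** In a 1:1 randomized trial any baseline difference between arms is due to chance, so a significance test on that difference is a poor gate for a covariate. The reason to adjust for screening WBIS is that it predicts later WBIS, and that is so whether or not the arms happen to differ.

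On the change reading, baseline already enters by subtraction. Subtraction fixes the slope of follow-up on baseline at 1. If the true slope is lower, a chance baseline gap is over-corrected; with a raw-score response it is not corrected at all. Either way the group estimate is noisier than it need be. In addition, the covariates of the primary model are settled only after the data are seen.

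**Working it through.** **Inputs from the documents.** Two-sided alpha 0.05 (7.2); 36 per arm, 20% attrition, SD 1, predicted reductions of 1.5 and 1 point, power stated for 1 point (7.1); entry at a WBIS mean of 4 or above (5.2) on a 1–7 scale (6.1).

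**Assumptions not in the documents.** 29 per arm analysed at week 12 (36 × 0.8 = 28.8). Population WBIS normal with SD 1 at both times, mean 4.5 or 5 at screening, population correlation *r* = 0.3, 0.5 or 0.7. Screening scores truncated to 4–7. Independent participants. Section 7.1 does not say whether its SD of 1 belongs to the score or to the change, so each is taken in turn and the results are scaled accordingly.

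**1. The plan's own figure.** SE = √(2/29) = 0.263. The noncentral t on 56 df gives power 96.3% at 1 point, in line with the stated 95%, and 46.5% at 0.5 point (1.5 − 1). No baseline covariate is needed to reach the stated figure.

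**2. How often screening WBIS enters under the two-test sentence.** A balance test at the 5% level triggers in 5% of trials, and the second test can only lower that. In simulation (40,000 trials per setting) it enters in 2.7–4.7% of trials (change) or 1.7–5.1% (raw), so it is left out in about 95–98%. Type I error on the change reading is 0.046–0.048.

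**3. Precision with baseline always in.** Truncation leaves the slope *b* = *r* and the residual variance 1 − *r*² unchanged, but cuts the baseline variance *v* from 1 to 0.441 (mean 4.5) or 0.520 (mean 5).

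- Unadjusted variance of change: (1 − *r*)²*v* + 1 − *r*².
- Unadjusted variance of the raw score: *r*²*v* + 1 − *r*².
- Adjusted SE, after scaling the unadjusted SD to 1: residual SD × √(2/29) × √(1 + 1/54). The last factor is the cost of estimating the slope.

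Example (mean 5, *r* = 0.5, change): unadjusted SD = √(0.25 × 0.520 + 0.75) = 0.938. Scaled residual SD = 0.866/0.938 = 0.923. SE = 0.923 × 0.263 × 1.009 = 0.245, down 6.8%. Power at 0.5 point is 51.9%.

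**4. Shift from a baseline gap.** Given a gap *g* in screening means, the change-score estimate moves by −(1 − *b*)*g* and the raw-score estimate by +*bg*. With 36 per arm, a 1-SE gap is √(2/36) = 0.236 baseline SD. The largest non-significant gap is t(0.975, 70 df) × 0.236 = 0.470 SD. In the example the scaled baseline SD is √0.520/0.938 = 0.769, so the shifts are 0.5 × 0.236 × 0.769 = 0.091 and 0.5 × 0.470 × 0.769 = 0.181 point.

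Change reading, all settings:

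| Mean | *r* | In-trial *r* | Adjusted SE (fall) | Power, 0.5 point | Shift, 1-SE gap | Shift, largest non-significant gap |
|---|---|---|---|---|---|---|
| 4.5 | 0.3 | 0.20 | 0.238 (9.3%) | 54.1% | 0.103 | 0.206 |
| 4.5 | 0.5 | 0.36 | 0.247 (5.8%) | 51.0% | 0.084 | 0.168 |
| 4.5 | 0.7 | 0.55 | 0.255 (2.8%) | 48.6% | 0.063 | 0.126 |
| 5 | 0.3 | 0.22 | 0.234 (10.8%) | 55.4% | 0.110 | 0.220 |
| 5 | 0.5 | 0.38 | 0.245 (6.8%) | 51.9% | 0.091 | 0.181 |
| 5 | 0.7 | 0.58 | 0.254 (3.4%) | 49.1% | 0.068 | 0.136 |

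Simulated power at 0.5 point agrees: 48.3–55.6% with baseline always in, against 46.0–47.1% under the two-test sentence across both readings. The mean absolute shift is the 1-SE shift × √(2/π), or 0.05–0.09 point.

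Raw reading: SE falls 1–18%, power at 0.5 point is 47–62%, and the largest non-significant gap shifts the estimate by 0.10–0.27 point in the opposite direction.

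At 1 point, adjusted power is 97–99% (change) or 97–99.6% (raw).

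Without the entry cut-off, adjusted power at 0.5 point would be 53–64% (change) or 50–75% (raw), so ignoring it overstates the gain.

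**5. Carry-over to the mixed model.** With baseline and baseline-by-time in the model and an unstructured covariance, the week-12 contrast equals the week-12 analysis of covariance (largest difference below 1e-13, with complete data or monotone dropout), so the week-12 gains carry over.

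**The case against.** The strongest reply is that nothing in the design fails. At the difference the trial is powered for, power only moves from 96% to 97–99% on the natural reading. The gain is visible at 0.5 point only because section 7.1 predicts 0.5 and powers for 1, which is a separate inconsistency; adjustment does not make the trial well powered for 0.5. All of this stands.

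The shift from a chance gap might be read as a second harm, a bias on top of lost precision. It is not. Over randomizations the shift averages to zero, and its spread is exactly the excess variance already counted in the standard error. The largest-gap figures are also extremes: near misses (baseline p between 0.05 and 0.15) occur in about 5% of trials in each direction.

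A reader might also infer that baseline WBIS is ignored. On the change reading it is not, because it enters every trial by subtraction.

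The two covariate sentences can be read together, with the second defining which variables count as relevant in the first. If they are read apart, they disagree on a variable that is imbalanced but unrelated to outcome. The first sentence, having no threshold, might also allow adjustment for a near miss. The shift figures therefore assume that the two-test sentence governs.

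Finally, treatment is delivered in groups (4.1) and section 7.1 mentions an ICC. Any variance between groups would dilute the percentage gain.

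What remains is that no passage makes screening WBIS a standing covariate, and that doing so costs almost nothing.

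**Conclusion.** This is a free improvement. The documents do not support a claim that the planned analysis is invalid, that type I error is inflated, or that the 95% power for 1 point is wrong.

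The supported point is a modest and avoidable loss of precision in the primary comparison, together with a covariate choice left to the data and an unnamed response. On the change reading the avoidable part of the standard error is about 3–11%. In a single trial the same loss typically appears as a shift of 0.06–0.11 point, and at most 0.13–0.22 point for a gap that escapes the balance test, against an SE of about 0.26 and a predicted difference of 0.5. With baseline in the model the shift is about zero.

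These sizes rest on the assumed correlation, population mean, truncated-normal shape and independence of participants. The direction does not: the change score loses precision whenever the slope differs from 1, and the raw score whenever it differs from 0.

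**What to change.** In section 7.2, write:

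> The response is change from screening WBIS at weeks 12 and 26. Screening WBIS and its interaction with time are fixed covariates regardless of baseline balance.

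With these terms, change and raw score give the same group estimate, since subtracting baseline only lowers its coefficient by 1 at each time point. The interaction is needed: with a single common slope when the true slopes are 0.6 at week 12 and 0.3 at week 26, the week-12 estimate moved by up to 0.18 point in a simulated trial (SD 0.03).

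Replace both balance-triggered sentences. Report baseline characteristics descriptively. Limit other covariates to ones named in advance, or use them only in sensitivity analyses.

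Section 7.2 applies the same methods to the other outcomes, so own-baseline adjustment may be carried over to those with a baseline measure. This is secondary to repairing the primary model, since section 7.1 states "All secondary outcomes will be considered exploratory". It cannot apply to treatment acceptability, which has no baseline value.

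Cost: a few sentences, two degrees of freedom and no new data.

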## 4. STUDY DESIGN

### 4.1 General Design

This is a randomized controlled trial to test the effects on WBI of a novel psychological intervention combined with standard BWL treatment, as compared to BWL alone. Participants will be a total of 72 men and women seeking weight loss, ages 18-65 years, with a body mass index (BMI) of 30 kg/m^2 or above, a history of experiencing weight bias, and elevated levels of WBI. Participants will attend a screening visit in which they will complete a behavioral evaluation with a psychologist and a medical history that will be reviewed by a nurse practitioner or physician. Questionnaires assessing experiences and internalization of weight bias, with confirmation by interviewer assessment during the behavioral evaluation, will be used to determine whether participants meet criteria for having high levels of WBI. Eligible consenting participants will be randomly assigned to the standard BWL intervention (n = 36) or the BWL + BIAS program (n = 36). All participants will attend weekly, 90-minute group meetings for 12 weeks (12 visits). In the BWL + BIAS intervention, 60 minutes will be devoted to BWL and 30 minutes to weight stigma. In the standard BWL treatment group, the additional 30 minutes will be devoted to sharing recipes and food preparation tips. Following 12 weeks of weight loss treatment, participants will attend group meetings focused on weight loss maintenance, every-other-week from weeks 13-16 (2 visits), and monthly from weeks 17-26 (2 visits). Maintenance sessions in the BWL + BIAS group will continue to incorporate discussion of WBI. Assessments – which include questionnaires and measurements of body weight – will occur at baseline and weeks 12 and 26. Additional assessments will also occur at week 52. Weight will be measured at every group meeting for clinical purposes.

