### **6.2 Randomization**

Following the screening visit, participants who meet all eligibility criteria and provide informed consent will be randomized to one of the two treatment groups in a 1:1 ratio by a biostatistician. Investigators and participants will not be blinded to participants' assigned

conditions.

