### **6.3 BWL Intervention**

Participants in this group will be provided with 12 weekly BWL sessions, based on the Diabetes Prevention Program (DPP) manual, followed by 2 every-other-week weight loss maintenance sessions and 2 monthly sessions (for a total of 16 visits over 26 weeks). A diet of 1200-1499 calories per day will be prescribed for participants < 250 lb, and 1500-1800 for those  $\geq 250$  lb. Participants will be instructed to eat a balanced deficit diet with approximately 15-20% of kcal from protein, 20-35% from fat (less than 10% from saturated fat), and the remainder from carbohydrates. Session topics during the first 12 weeks will include self-monitoring, stimulus control, slowing eating, social support, cognitive restructuring, portion sizes, and goal-setting. Those during weeks 13-26 will focus on continued self-monitoring and skills required for weight loss maintenance and relapse prevention. BWL sessions will last 60 minutes, with an additional 30 minutes devoted to discussing recipes and food preparation.

Physical activity will be prescribed at a level consistent with data showing that  $\geq 250$  min/wk is associated with improved long-term weight loss. Activity will begin at week 2 with 60 min/wk, and will gradually progress by 10 minutes over 1-2 week intervals until achieving 150 min/wk by week 12, and 200-250 min/wk by week 26. Participants will be instructed to spread the 150-250 minute doses of activity equally across at least 5 days, and to accumulate their structured physical activity in bouts that are  $\geq 10$  minutes in duration. Moderate intensity will be prescribed with an emphasis on walking; the vast majority of our research participants self-select this form of activity.

Participants who cannot attend any given group session will be offered a brief (10-20 minute) make-up session during the week with the group leader or a study staff member. Participants may also meet briefly with the group leader individually, outside of group sessions, up to 3 times during the initial 12-week study period if they have not lost at least 1% of their body weight by week 4, report difficulty controlling their eating, or describe other challenges preventing them from adhering to the program that cannot be fully covered during group sessions.

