### **6.4 BWL + BIAS Intervention**

Participants in this group will receive the same BWL program described above, which will be combined with a stigma-reduction intervention. During the initial 12 weeks, the 60-minute BWL sessions will be followed by 30 minutes devoted to stigma-related content. Session topics will be based on those tested in a previous pilot study, including: psychoeducation about weight and weight stigma; challenging myths and cognitive distortions related to weight; strategies for coping with instances of stigma; and increasing empowerment and body esteem. The effects of weight stigma on health behaviors will be discussed, and sessions will focus specifically on helping participants overcome stigma-related barriers to weight management. For example, they will be given strategies to cope with anticipated stigma while exercising in public spaces (e.g., while walking), as well as to challenge self-critical beliefs (e.g., that they are lazy) which may otherwise lead them to avoid engaging in physical activity. These concrete strategies, along with reducing WBI and improving self-confidence, are intended to increase participants' self-efficacy for and engagement in weight management behaviors. In the every-other-week and monthly weight loss maintenance sessions from weeks 13-26, strategies for coping with weight

stigma and challenging internalized beliefs will be reviewed, and participants will be encouraged to use these strategies specifically in the context of weight management.

As with the BWL Intervention, participants who cannot attend group sessions or are experiencing difficulties adhering to the program will be eligible for brief individual meetings with the group leader or study staff (as described above).

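### Both arms are treated in therapy groups, but the section 7.2 model has no therapy-group term, and the ICC in section 7.1 has no value or level to show whether clustering was allowed for

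*Combined protocol and SAP*

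**What the plan says.** **Randomization.** Section 6.2 allocates individuals: eligible participants "will be randomized to one of the two treatment groups in a 1:1 ratio by a biostatistician".

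**Delivery.** Section 4.1 puts everyone in groups: "All participants will attend weekly, 90-minute group meetings for 12 weeks (12 visits". After week 12, "participants will attend group meetings focused on weight loss maintenance", ending at week 26. Section 6.4 gives the experimental arm the same group programme plus the stigma content: "Participants in this group will receive the same BWL program described above, which will be combined with a stigma-reduction intervention". Groups have a leader; section 6.3 offers those who miss a meeting a brief "make-up session during the week with the group leader or a study staff member". The number and size of groups, and how leaders are assigned, are not stated.

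**Analysis.** Section 7.2 treats the group meeting as the unit of treatment: randomized participants who "did not attend a group meeting will not be included in the analyses, as they will not have received a dose of treatment". In the model, "a mixed effects model will be fit with Treatment Group" is the between-subjects factor and time (weeks 12 and 26) the within-subjects factor. The section also provides the group-by-time interaction, baseline covariates that are imbalanced and related to the outcome, and a covariance structure selected by criteria such as AIC. None of these is tied to therapy group, cohort or leader. The same methods are carried over to the other outcomes.

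**Sample size.** Section 7.1 says "Estimated group means, attrition rate, intraclass correlation (ICC), and variances were derived from data from prior studies conducted at our Center". It gives no value for the ICC, does not say whether it is between members of a therapy group or between repeated measures on one person, and gives no group size or design effect.

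**The concern.** People who meet weekly in the same room, with the same leader and the same discussion, may come to resemble one another on the outcome. That is plausible for WBIS, because group discussion of stigma is part of what is being tested. Individual randomization does not remove this correlation, because it arises after allocation.

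If it is positive and the model ignores it, the variance of the arm contrast is understated. The 95% interval is then too narrow and the test rejects a true null more often than 5%. Section 7.1 declares all secondary outcomes exploratory, so the confirmatory consequence falls on one quantity, the week-12 WBIS contrast. The main harm is false positives and poor coverage, not missed effects.

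**Working it through.** **Inputs from the documents.** 36 per arm, 20% attrition, a 1-point difference and SD 1 (section 7.1); two-sided alpha 0.05 (section 7.2). The 1-point difference is used because the stated power refers to it. Section 7.1's predicted reductions of 1.5 and 1 differ by only 0.5, which is a separate matter.

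**Inputs assumed.** Therapy groups per arm, k = 2 to 6, and therapy-group ICC, ρ = 0 to 0.05. The documents give neither.

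**Step 1. Reproduce the stated power without clustering.** Completers per arm: 36 × 0.8 = 28.8. Noncentrality: 1 / √(2/28.8) = 3.795. With 2 × 28.8 − 2 = 55.6 df, the critical value is 2.004 and the power is 96.2% (96.7% by the normal approximation). The stated 95% is reached with no clustering.

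**Step 2. Reproduce it with a small ICC.** Completers per group: m = 28.8/k. Design effect: D = 1 + (m − 1)ρ. The noncentrality becomes 3.795/√D; the individual-level df are kept.

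| k | m | ρ | D | Power |
|---|---|---|---|---|
| 2 | 14.4 | 0.005 | 1.067 | 95.0% |
| 3 | 9.6 | 0.01 | 1.086 | 94.7% |
| 4 | 7.2 | 0.01 | 1.062 | 95.1% |
| 5 | 5.76 | 0.01 | 1.048 | 95.4% |
| 6 | 4.8 | 0.02 | 1.076 | 94.9% |

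The stated figure fits a small allowance at least as well as none. It does not show which was used.

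**Step 3. Type I error of the unclustered week-12 test.** Approximately 2 × [1 − Φ(1.96/√D)]. For k = 3 and ρ = 0.05: D = 1 + 8.6 × 0.05 = 1.43; 1.96/√1.43 = 1.639; type I error 10.1%. A simulation (200,000 runs per cell, 29 completers per arm, near-equal group sizes, two-sample t-test on week-12 change) agrees with the formula within 0.3 percentage points in every cell below. That test equals the week-12 arm contrast with complete data and an unstructured covariance. Simulated values:

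| ρ | k = 2 | 3 | 4 | 5 | 6 |
|---|---|---|---|---|---|
| 0 | 5.0% | 5.0% | 5.0% | 5.0% | 5.1% |
| 0.01 | 6.6% | 6.0% | 5.7% | 5.6% | 5.5% |
| 0.02 | 8.2% | 7.1% | 6.5% | 6.1% | 6.0% |
| 0.05 | 13.2% | 10.3% | 8.9% | 7.8% | 7.2% |

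Coverage of the nominal 95% interval is 100% minus these values, so about 87-93% at ρ = 0.05. In the same simulation the modelled standard error falls short by 2-6% at ρ = 0.01 and 9-24% at ρ = 0.05.

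**Step 4. What a clustered analysis costs.** With df taken from the number of groups, 2(k − 1), and ρ = 0, power for 1 point is 53 / 81 / 88 / 91 / 93% for k = 2 / 3 / 4 / 5 / 6. The probability that the group variance is estimated at zero is P[F(2k − 2, 58 − 2k) < (1 − ρ)/(1 + (29/k − 1)ρ)]. Across k this is 50-58% at ρ = 0.01 and 37-43% at ρ = 0.05.

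**The case against.** **The ICC may already cover this.** Section 7.1 says an ICC was an input, and Step 2 shows that a small therapy-group ICC fits the stated power. This stands as far as it goes. A reader might infer from the 96.2% that clustering was left out of the sample size; the documents do not support that, because rounding down and a small allowance both lead to 95%. But an ICC in section 7.1, even if it is the right one, does not correct the standard error in section 7.2.

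**The AIC choice could bring in clustering.** The choice is described for a model with repeated time points and names no therapy-group level. It would ordinarily be read as choosing among within-person structures.

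**The larger error rates are assumption only.** This stands. A reader might take 13%, or the 10-21% that the same simulation gives at ICC 0.10, as the trial's actual error rate. No ICC value or group count in the documents supports either figure. If the ICC behind section 7.1 is a small therapy-group ICC, the inflation is minor.

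**A clustered model is weak with few groups.** This also stands. Step 4 shows low power with 2 or 3 groups per arm and an ICC estimate that is often zero. It is a reason to fix the roles of the two models in advance, not to leave clustering unaddressed.

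**Conclusion.** The point holds, with a size that the documents leave open. Individual randomization, group treatment in both arms and the absence of a therapy-group term are all in the text. Only the direction of the effect is established: for any positive therapy-group ICC, the section 7.2 model as written understates the standard error of the week-12 WBIS contrast. With 2 to 6 groups per arm assumed, type I error is about 5.5-6.6% at ICC 0.01, which is minor, and about 7-13% at ICC 0.05, which is not. At ICC zero there is no harm.

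The stated 95% does not show whether clustering was allowed for. Nor do the documents support concluding that the primary analysis is invalid. They support saying that it rests on an independence assumption that is neither stated nor checked. The change is worth making because the primary inference is exposed and the cost is small.

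**What to change.** 1. **Record** each participant's therapy group.
2. **In section 7.2, before outcome data are analysed**, pre-specify an analysis of the week-12 WBIS contrast with a random intercept for therapy group nested in arm and small-sample df (for example Kenward-Roger). Report its estimate, 95% interval and estimated ICC beside the unclustered result.
3. **Fix a reading rule in advance.** If the clustered interval includes zero and the unclustered one does not, report the primary result as not robust to clustering by therapy group. Without such a rule, a sensitivity analysis leaves the false-positive risk where it was.
4. **State which model is primary**, from the planned number of groups. Where to draw the line is a judgement on which statisticians may differ; the power figures in Step 4 inform it. With one group per arm the term cannot be estimated, and the result should carry that caveat.
5. **In section 7.1**, give the ICC's level and value and the planned group size, or say that the 95% assumes no clustering by therapy group.

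**Cost.** One recorded variable, one additional model and some wording; no new assessments. The clustered intervals will be wider. With few groups the clustered analysis has low power (about 53% with 2 groups per arm and 81% with 3, for 1 point at ICC zero). The ICC estimate will be imprecise, so an estimate of zero should not be read as showing that clustering is absent.
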